6.5 Concomitant Therapy

Throughout the study, investigators may prescribe any concomitant medications or treatments deemed necessary to provide adequate supportive care except for those listed in Section 6.9.

All prescription and nonprescription concomitant medication administered from the signing of the main informed consent, on an ongoing basis at enrollment, as well as changes in such concomitant medication, and, any new concomitant medication taken while the subject is on study, should be recorded on the appropriate CRF until approximately 30 (+7) days after the last dose of talimogene laherparepvec or pembrolizumab, whichever is later. The therapy name, indication, dose, unit, frequency, start date, and stop date will be collected.

Investigators should use supportive care agents in compliance with their respective regional label. Investigators may not use supportive care agents as part of a separate clinical trial.

6.6 Other Treatment Procedures

As of Protocol Amendment 6 (dated 26 October 2021), intrahepatic injections of talimogene laherparepvec and liver biopsies are no longer performed in this study.

Treatment with talimogene laherparepvec and pembrolizumab in the combination setting may result in the reduction of tumor burden such that surgical resection of previously unresected lesion becomes possible. Investigators may choose to resect lesions which become suitable for resection to render the subject free of macroscopic disease. Additionally, biopsies may be taken of liver lesions for tumor analysis during study. In the event of a CR, any residual target lesions must be documented by representative biopsy to not contain viable tumor. If a subject undergoes resection of the lesion in the event other than CR, the investigator or designee should notify the sponsor medical monitor and the procedure should be recorded in the source document and CRF. In these instances, if the response of other lesions is at least PR (if other lesions remain), the response should be designated PR with the date of surgery as the date of response. If no residual disease remains following surgery, this should also be noted in the CRF, the response definition again being PR if viable cancer was noted in the surgical

specimen, and CR if no viable cancer was identified in the surgical specimen. Best response of CR or PR due to surgeries will not be considered for assessment of ORR or BOR.

Palliative surgery for relief of symptoms is allowed. Treatment with talimogene laherparepvec and/or pembrolizumab should be held, and the investigator or designee should notify the sponsor as soon as possible. Subjects may be allowed to remain on study after discussion between the sponsor medical monitor and the investigator. Investigator must get approval from the sponsor medical monitor before resuming talimogene laherparepvec and/or pembrolizumab.

Local palliative radiation treatment for relief of various symptoms, including but not limited to bleeding or pain associated with the underlying disease will be permitted at any time during the study. Subjects with local symptoms suggestive of disease progression should be evaluated for tumor response per modified irRC-RECIST (see [Appendix D](#)) prior to the administration of palliative radiotherapy. If a subject undergoes local radiation, the investigator or designee should notify the sponsor medical monitor as soon as possible and the treatment should be recorded in the source document and CRF.

If a subject demonstrates evidence of new or worsening CNS metastases, talimogene laherparepvec and/or pembrolizumab treatment should be withheld and the investigator or designee should notify the sponsor's medical monitor as soon as possible. Subjects may be allowed to remain on study after discussion between the sponsor medical monitor and the investigator to determine the appropriateness of treatment resumption provided CNS lesions can be treated with stereotactic radiotherapy (including Gamma Knife), whole brain radiation, or craniotomy and if there is no change in the baseline ECOG performance status. Subjects may be allowed to resume talimogene laherparepvec treatment per Section 6.2.1 following treatment of CNS metastases while receiving dexamethasone or a similar corticosteroid at no more than 1.5 mg dexamethasone (or 10 mg prednisone) per day. If higher doses of corticosteroid are used, talimogene laherparepvec must be held until that dose level is reached during the period of steroid tapering.

If a subject with confirmed PD (ie, two consecutive tumor assessments at least 4 weeks [28 days] apart demonstrating PD) is clinically stable or clinically improved, and there is no further increase in tumor burden at the confirmatory assessments (assessed by the

investigator and site radiologist, if applicable), an exception may be considered to continue treatment upon consultation with the sponsor medical monitor.

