If a subject is classified as having PD at a postbaseline tumor assessment, then confirmation of PD by a second assessment ≥ 4 weeks (28 days) later in the absence of rapid clinical deterioration (ie, rapid decline in performance status) or symptomatic disease requiring rapid initiation of alternative systemic anti-cancer therapy is required. The definition of confirmation of progression represents a $\geq 20\%$ and at least 5 mm absolute increase in the total tumor burden (ie, the sum of diameters of target lesions plus up to 10 [maximum 5 per organ] new measurable lesions) compared to the nadir at two consecutive time-points at least 4 weeks (28 days) apart (with the date of progression considered to be the time of the initial evaluation showing PD). It is recommended that this be done at the discretion of the investigator because follow-up with observation alone may not be appropriate for subjects with a rapid decline in performance status. Confirmation of PD allows for the capture of all observed responses using the irRC-RECIST as most of these late responding subjects have a trend toward response within 4 weeks (28 days) after initial PD.

Subjects with a global deterioration of health status requiring discontinuation of treatment without objective evidence of PD at the time should have the reason for treatment discontinuation specified. Every effort should be made to document the objective progression even after discontinuation of treatment.

Determining a New Nadir After Intervention-therapy:

After the intervention-therapy for liver lesions is completed, subjects will undergo radiological imaging by either CT or MRI or US according to the schedule defined in Section 7 of the protocol. The first post intervention tumor assessment will provide the “new nadir” from which progression will be assessed. Any remaining sites of disease

must continue to be followed as target and non-target lesions as designated at study screening. Post intervention tumor assessment will be performed until confirmed PD, according to the schedule of the study protocol.

Subjects who have had Complete Removal of the Lesion will be Evaluated as Follows:

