The completely resected lesion should continue to be documented on the case report forms (CRFs) and assigned a default code of absent (for nontarget lesions) or a value of 0 mm for the longest diameter for the purpose of calculating the sum of the diameters (for target lesion), and determining the post intervention-therapy response. This will allow continued response determination from screening.

If the resected lesion contained no tumor under pathology evaluation, subsequent tumor assessments post-procedure may be used for tumor burden calculations and/or determination of response. If the resected lesion contained tumor or pathology results were unknown, the recorded tumor assessments post-procedure may be used for tumor burden calculations, but determination of response will be considered unevaluable (UE) for response except in the case of PD. If the new tumor burden post-procedure is lower than the nadir before the procedure, then the new nadir will be set to the post-procedure tumor burden. Otherwise, the previous pre-procedure nadir will be retained as the nadir. Subsequent assessments for PD will be determined from the nadir.

Guidance on quantitative/qualitative reporting of fully resected lymph nodes is below (see [Table 21](#)).

If new radiographic imaging findings develop at the surgical/treatment site that were not present on the immediate post intervention-therapy imaging assessments and are indicative of tumor recurrence, the tumor will be considered a new lesion, and measured accordingly, with the response assessed as PD if increase in tumor burden $\geq 20\%$ and at least 5 mm absolute increase relative to nadir compared with the first post intervention-therapy nadir at two time points at least 4 weeks (28 days) apart.

Table 21. Quantitative/Qualitative Reporting of Fully Resected Lymph Nodes

Lymph Node Type/Presence	Contained Cancer Under Pathology Evaluation?	Quantitative/qualitative Reporting
Target lymph node previously present	Yes/Unknown	If measurement available: Actual short axis
		If measurement not available: 10 mm short axis
	No	If measurement available: Actual short axis
		If measurement not available: 9 mm short axis
Non-target lymph node previously present	Yes/Unknown	Present
	No	Absent
Lymph node not previously present	Yes/Unknown	If measurement available and short axis < 15 mm: New non-measurable lymph node ^a
		If measurement available and short axis ≥ 15 mm: please enter actual measurements (do not default to 10 mm) ^a

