## Best overall response (BOR) per Modified irRC-RECIST

Best overall response (BOR) of complete response (CR), partial response (PR), stable disease (SD), progressive disease (PD) or un-evaluable (UE) will be derived based on investigator assessment using modified irRC-RECIST as defined in protocol Appendix D.

Overall visit response assessments occurring after the start of the first subsequent anticancer therapy **will not be included. With the exception of a PD observation, the overall visit response** occurring on or after complete or partial removal/reduction of any target lesion which contained cancer on pathology evaluation or pathology results were unknown, will not be included. Consecutive confirmation of CR, PR, and PD is required where the second overall response must be at least 28 days from the first, the only exception being when the investigator reports that an initial PD cannot be confirmed due to rapid clinical deterioration. The following will be considered a confirmed PR: CR followed by PR or PR followed by CR.

BOR is defined as the best visit response in the following order: CR, PR, SD, PD, or UE (see [Table 1](#)). BOR is defined as SD if the best overall visit response is an unconfirmed CR or PR, and UE if it is either SD earlier than 77 days after first dose date or an unconfirmed PD when confirmation of PD is required (ie, initial PD without rapid clinical deterioration).

Table 1. Matrix of Determining BOR per Modified irRC-RECIST

Visit Overall Response Sequence	Examples	Best Overall Response	Confirmation specifications
*, CR, CR,*	PR, CR, CR CR, CR, PD	CR	The confirmatory CR must be at least 4 weeks (28 days) later; a subsequent CR within 28 days will not be valid for

			confirmation and will be ignored; the CR will also not be confirmed if there is a subsequent PR/SD/PD at any time prior to the next CR.
* , PR, PR, *  * , PR, CR/PR, non-CR, *  * ,CR, PR,*	PR, PR, PD PR, CR, PD  CR, PR, PD	PR	Criteria for BOR=CR not met. The confirmatory PR/CR must be no less than 4 weeks (28 days) later; a subsequent PR/CR within 28 days will not be valid for confirmation and will be ignored; the PR will also not be confirmed if there is a subsequent SD/PD at any time prior to the next PR/CR.
* , SD, *  * ,CR, non-PR/CR, *  * ,PR, non-PR/CR, *	CR PD, CR PR PD, PR, SD SD PD,SD,PD	SD	Criteria for BOR=CR or PR not met. SD must be $\geq 77$ days from the date of first dose; however, this is not required for an unconfirmed CR/PR.

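### Protocol 6.6 keeps responses due to surgery out of ORR with no pathology exception, but Appendix D and the SAP let a response first reached after a pathology-negative resection count

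*Protocol*

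**What the plan says.** **Protocol 6.6.** Investigators may resect lesions that become resectable. If the other lesions are at least in PR, "the response should be designated PR with the date of surgery as the date of response". If nothing remains after surgery, the response is PR when the specimen held viable cancer and "CR if no viable cancer was identified in the surgical specimen". The next sentence is "Best response of CR or PR due to surgeries will not be considered for assessment of ORR or BOR".

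**Protocol Appendix D, complete removal.** A resected target lesion is given "a value of 0 mm for the longest diameter for the purpose of calculating the sum of the diameters". If the specimen held no tumor, "subsequent tumor assessments post-procedure may be used for tumor burden calculations and/or determination of response". If it held tumor or pathology is unknown, response is unevaluable except for PD. The subsection on partial removal has the same pathology rule.

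**SAP section 5, BOR.** BOR is derived from Appendix D. Apart from PD, a visit response is left out when it is one "occurring on or after complete or partial removal/reduction of any target lesion which contained cancer on pathology evaluation or pathology results were unknown". Pathology-negative resections are not mentioned, so those visits stay in. The ORR definition adds no surgical exclusion. SAP section 6.11 expressly exempts pathology-negative resection from censoring at lesion level. SAP section 10 lists no change from the protocol, and Table 9-1 shows N/A for sensitivity analysis of ORR.

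**Nadir, Appendix D.** After intervention for liver lesions, "The first post intervention tumor assessment will provide the" new nadir. The later subsections on complete and partial removal reset the nadir only if the post-procedure burden is lower: "Otherwise, the previous pre-procedure nadir will be retained as the nadir".

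**The concern.** ORR is the Part 2 primary efficacy endpoint, and each arm is decided by a small count of responders. Take a subject with stable disease whose residual target lesion is resected and found free of tumor. Scored at 0 mm, that lesion can bring the sum of diameters below the PR threshold, and a scan at least 28 days later can confirm it. Appendix D and the SAP then allow a responder; 6.6 read as written does not. Two analysts, each following a current document, could report different counts, and no planned sensitivity analysis would show the difference. Response is investigator-assessed in an open-label trial, so the rule should not be settled after the data are seen.

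**Working it through.** **1. The rules side by side**

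| Situation | Protocol 6.6 | Appendix D | SAP section 5 |
|---|---|---|---|
| Response met and confirmed before surgery | counts | counts | counts |
| Threshold first reached because a target lesion is scored as removed; tumor in specimen or pathology unknown | not counted | unevaluable unless PD | visit dropped unless PD |
| Same, no tumor in specimen | not counted | may count | visit kept, counts |
| Threshold first reached because a new measurable lesion is removed; tumor in specimen or pathology unknown | not counted | unevaluable unless PD | visit kept, counts |

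The third row is the main conflict. The fourth is a gap in the SAP alone: tumor burden is the target sum plus new measurable lesions, but the SAP exclusion names only target lesions.

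Non-target lesions differ. In Appendix D Table 20, a fall in tumor burden of at least 30% is PR whatever the non-target status, and a 100% fall with non-target disease still present is already PR. ORR counts CR and PR alike. Removing a non-target lesion can change PR to CR in BOR, but not the responder count.

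**2. The plan's own figures**

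Inputs (Protocol 10.2): 10 subjects in Stage 1, continue with 2 or more responders; 11 more in Stage 2; reject with 6 or more of 21; null 10%, alternative 40%.

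- P(stop at Stage 1) = (1−p)^10 + 10p(1−p)^9. At p = 0.10: 0.3487 + 0.3874 = 0.736. At p = 0.40: 0.0060 + 0.0403 = 0.046.
- P(reject) = Σ over i = 2 to 10 of P(X1 = i) × P(X2 ≥ 6−i), with X1 ~ Bin(10, p) and X2 ~ Bin(11, p). At p = 0.10: 0.0133. At p = 0.40: 0.884.

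These match the stated 73.6%, 4.6%, 1.3% and 88.4%. The design arithmetic is sound.

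**3. One disputed subject at the boundary**

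- 6/21 = 28.6%, Clopper-Pearson 95% CI 11.3% to 52.2%: reject.
- 5/21 = 23.8%, CI 8.2% to 47.2%: do not reject.
- Lower limits that allow for the two stages are 11.5% and 8.6%, with the same decisions.

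At Stage 1, one such subject likewise separates 1 from 2 responders in 10.

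**4. If such cases were not rare (assumption)**

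The documents give no rate. Let s be the share of all subjects who respond only through a pathology-negative resection, treated the same way at both stages.

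| s | P(reject) if non-surgical ORR is 10% and they are counted (rate 10% + s) | Power if the 40% includes them and they are excluded (rate 40% − s) |
|---|---|---|
| 2% | 3.0% | 84.6% |
| 5% | 7.7% | 77.3% |
| 10% | 21.6% | 61.0% |

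**5. Nadir**

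Take a hypothetical earlier nadir of 50 mm and a first post-procedure burden of 55 mm. PD needs a rise of at least 20% and 5 mm. If the first post-procedure scan sets the nadir, PD is reached at 1.2 × 55 = 66 mm. If the lower value is kept, it is reached at 1.2 × 50 = 60 mm.

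**The case against.** The texts can be reconciled. The phrase *due to surgeries* is undefined. Section 6.6 requires biopsy proof that residual target lesions in a CR hold no viable tumor, and Appendix D recommends biopsy to settle a CR. On that view, a tumor-free specimen shows that treatment cleared the lesion, and Appendix D and the SAP merely make the 6.6 phrase operational through pathology. The SAP also sends the analyst to Appendix D, so in practice one rule would be used.

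This is a fair reading, but 6.6 does not state it, and its preceding sentence lists the no-viable-cancer CR among the post-surgical responses. Appendix D is also only permissive.

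Other parts of the objection stand. The conflict does not touch responses confirmed before surgery. Section 6.6 says resection may become possible, not that it is expected. The 6/21 versus 5/21 contrast would hold for any one misclassified responder. Enrollment has stopped with 53 subjects in Part 2 over six arms. At most two arms can have reached 21 (2 × 21 = 42; 3 × 21 = 63), and the documents do not show that any did.

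**Conclusion.** The concern holds in a limited form. For a subject who first meets response only after a pathology-negative resection, 6.6 and the Appendix D/SAP rule give different answers on the primary endpoint, and the SAP declares no departure. In addition, the SAP exclusion omits resected new measurable lesions. Where an arm reaches 21 subjects, one such subject can reverse its conclusion. How often this happens is unknown, and the table for s = 2% to 10% shows only what assumed rates would do.

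A reader might infer three stronger points that the documents do not support:

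- That removing a cancerous non-target lesion inflates ORR. It affects only the CR or PR label in BOR.
- That the nadir conflict changes ORR. Response is judged against baseline and only PD against nadir. The two statements overlap only for liver-lesion interventions, and in the 50-to-55 mm example disease must have grown elsewhere, because a fully resected target lesion scores 0 mm. What can differ is the PD date, and with it PFS, DOR and DRR.
- That 6.6 bars every response seen after a resection. It bars those due to surgery.

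**What to change.** State one rule in Protocol 6.6, Appendix D and SAP section 5, before the primary-analysis database lock.

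- **Primary ORR, following 6.6:** do not count a CR or PR whose threshold is first reached only because a resected target or new measurable lesion is scored as removed, whatever the pathology. Keep responses met and confirmed before surgery, and responses met without the resected lesion's contribution. One way to program this is to hold the resected lesion at its last pre-surgery measurement and check whether the threshold is still met.
- **BOR:** do not upgrade PR to CR because a non-target lesion was resected.
- **Sensitivity analysis:** replace N/A in SAP Table 9-1 with ORR counting pathology-negative post-resection responses. If the sponsor prefers that version as primary, amend 6.6 or list the departure in SAP section 10.
- **Nadir:** the sponsor must reconcile the two Appendix D statements for liver-lesion interventions. Confirmed PD also ends talimogene laherparepvec treatment under Protocol 6.2.1.2, so this review does not choose between them.

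The cost is wording in three places, one derivation and one table row, with no new data. The reported ORR may be slightly lower than under the SAP as it stands.

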6.9 Excluded Treatments and/or Procedures During Study Period

Subjects must not use any of the following therapies during screening or treatment period (including retreatment for post-CR relapse) of this trial:

- investigational agents (other than pembrolizumab and talimogene laherparepvec) or procedures
- warfarin. Other anticoagulants (ie. low molecular weight heparins, non-steroidal anti-inflammatory drugs) that do not prolong the PT/INR may be administered after investigator discussion with the sponsor and as long as there is adherence to institutional guidelines requiring their withholding for interventional radiology procedures.
- concurrent experimental or approved anti-tumor therapies or biological therapy other than study drug and radiation therapy required for palliation (as noted in Section 6.5)

Note: Radiation therapy to a symptomatic solitary lesion or to the brain may be considered on an exceptional case by case basis after consultation with Sponsor. The subject must have clear measurable disease outside the radiated field. Administration of palliative radiation therapy will be considered clinical progression for the purposes of determining PFS.

- immunotherapy not specified in this protocol
- chemotherapy not specified in this protocol

- chronic oral or systemic steroid medication use at a dose of >10 mg/day of prednisone (1.5 mg/day dexamethasone) or equivalent (with the exception of treatment for adverse events [see Section 6.2.1.2] and CNS metastases [see Section 6.5]). Steroids with low systemic absorption [eg, triamcinolone hexacetonide] injected into a joint space, and intermittent use of steroid inhalers or topical steroid is allowed).
- antiherpetic drugs, except those topically administered
- live vaccines within 30 days prior to the first dose of trial treatment and while participating in the trial. Examples of live vaccines include, but are not limited to, the following: measles, mumps, rubella, chicken pox, yellow fever, rabies, Bacillus Calmette-Guerin (BCG), and typhoid (oral) vaccine. Seasonal influenza vaccines for injection are generally killed virus vaccines and are allowed. However, intranasal influenza vaccines (eg, Flu - Mist[®]) are live attenuated vaccines, and are not allowed.
- any surgery for cancer (other than the exceptions noted in Section 6.6)

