*** Bone Lesions:**

- Bone scans, PET scans or plain films are not considered adequate imaging techniques to measure bone lesions. However, these techniques can be used to confirm the presence or absence of bone lesions.
- Osteolytic (lytic) bone lesions or mixed lytic-blastic lesions, with identifiable soft tissue components, that can be evaluated by cross-sectional imaging technique such as CT or MRI can be considered as measurable lesions if the soft tissue component meets the definition of measurability described above. Only the soft tissue component of the bone lesion should be measured.
- Many osteoblastic (blastic) bone abnormalities can be benign and should not be selected as baseline lesions. An isolated new small blastic lesion should not be selected as a new lesion unless there is demonstrated growth on subsequent scans. Multiple new blastic lesions that are clearly cancerous may be considered for new lesions.

Cystic Lesions:

- Lesions that meet the criteria for radiographically defined simple cysts should not be considered as malignant lesions (neither measurable or non-measurable) since they are, by definition, simple cysts.
- Cystic lesions thought to represent cystic metastases can be considered as measurable lesions, if they meet the definition of measurability described above. However, if non-cystic lesions are present in the same subject, these are preferred for selection as target lesions. If a cystic lesion is clearly cancerous and has both cystic and solid components, then the complete lesion should be measured including both components without excluding the cystic portion of a cystic tumor lesion when measuring.

Lesions with Prior Local Treatment:

Tumor lesions situated in a previously irradiated area, or an area subject to other loco-regional therapy, should not be considered measurable unless there has been demonstrated progression in the lesion.

Baseline Documentation of “Target” and “Non-Target” Lesions:

Baseline evaluations will be used to prospectively identify all sites of disease present as close as possible to the enrollment and never more than 4 weeks before the enrollment date. Sites of disease will be characterized as either target or non-target lesions.

Baseline Documentation of Target Lesions:

Up to 10 target lesions (a maximum of 5 per organ) will be chosen to measure over the course of therapy. Pathological lymph nodes that are defined as measurable must meet

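### The SAP has no rule for response scans after palliative radiotherapy to a target lesion, so radiation shrinkage can count in the primary ORR; its PFS definition also omits the protocol's radiation rule

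*Protocol*

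**What the plan says.** **When radiotherapy is allowed.** Protocol 6.6 covers "Local palliative radiation treatment for relief of various symptoms, including but not limited to bleeding or pain" and says that such treatment "associated with the underlying disease will be permitted at any time during the study". It does not say which lesions may be irradiated. It adds that "Subjects with local symptoms suggestive of disease progression should be evaluated for tumor response per modified irRC-RECIST" before radiotherapy, and says nothing about scans afterwards. Protocol 6.9 is tighter: radiation to a symptomatic solitary lesion or to the brain "may be considered on an exceptional case by case basis after consultation with Sponsor", and "The subject must have clear measurable disease outside the radiated field".

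**How it enters the endpoints.** For PFS, Protocol 6.9 states: "Administration of palliative radiation therapy will be considered clinical progression for the purposes of determining PFS". Neither section has a response rule for radiation. For surgery, Protocol 6.6 does have one: a CR or PR produced by surgery does not count in ORR or BOR.

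**What the SAP does.** The BOR definition in SAP Section 5 leaves out two kinds of visit:

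- "Overall visit response assessments occurring after the start of the first subsequent anticancer therapy";
- visits, other than PD, on or after the removal or reduction of a target lesion that had cancer on pathology, or whose pathology is unknown.

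The ORR definition stops counting at subsequent anticancer therapy or data cutoff. The PFS definition has two events, confirmed PD and death. Radiotherapy is not named in any of these.

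**Earlier radiation.** Protocol Appendix D says that lesions in a previously irradiated area "should not be considered measurable unless there has been demonstrated progression in the lesion".

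**The concern.** The protocol accepts in three places that local treatment can distort tumor measurement or mark failure. Surgery-driven responses do not count, previously irradiated lesions are not measurable without progression, and palliative radiation ends PFS. The effect of on-study radiation on response is the one case left without a rule.

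That case bears on the primary endpoint. Part 2 ORR is open-label (Protocol 5.1), investigator-assessed (SAP 9.1) and has no sensitivity analysis (SAP Table 9-1). If an irradiated target lesion shrinks and stays in the sum of diameters, the error in ORR is upward, towards declaring an arm active. The Stage 1 rule is also exposed, because it uses unconfirmed responses. The requirement to confirm at 28 days or later, which protects the final count from transient changes, would not remove lasting radiation shrinkage.

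For PFS the two documents disagree: the same event is progression in Protocol 6.9 and has no role in the SAP definition.

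**Working it through.** **1. The plan's own figures.** From Protocol 10.2 and SAP 3.2: 10 subjects in Stage 1, continue with at least 2 responders; 11 more in Stage 2; reject the 10% null with at least 6 confirmed responders of 21; alternative 40%.

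P(reject) = Σ over x = 2 to 10 of P[Bin(10, p) = x] × P[Bin(11, p) ≥ 6 − x]

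| Quantity | Plan | Recomputed |
|---|---|---|
| One-sided alpha, p = 0.10 | 1.3% | 1.33% |
| Power, p = 0.40 | 88.4% | 88.39% |
| Stop at Stage 1, p = 0.10 | 73.6% | 73.6% |
| Stop at Stage 1, p = 0.40 | 4.6% | 4.6% |

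The design reproduces.

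**2. What one subject does.** Exact (Clopper-Pearson) 95% lower limits: 5/21 = 23.8%, limit 8.2%, not above 10%; 6/21 = 28.6%, limit 11.3%, above 10%. At Stage 1, 1/10 closes the arm and 2/10 opens Stage 2.

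**3. Can radiation alone make a PR?** Appendix D requires a fall of at least 30% in tumor burden. Illustration: two equal target lesions, one irradiated and shrinking by 60%, the other unchanged, no new measurable lesions. Burden becomes (1 + 0.4)/2 = 0.70, a 30% fall and so a PR if confirmed. With five equal lesions and one disappearing completely, burden is 4/5 = 0.80, a 20% fall and no PR. It is possible with few target lesions and harder with many; Appendix D allows up to 10.

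**4. Sensitivity of alpha.** The documents give no frequency, so this is an assumed model. Let f be the share of non-responders with an irradiated target lesion, and s the chance that this yields a counted response. Apply the same rate at both stages: p = 0.10 + 0.90 × f × s.

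| f × s (assumed) | Apparent ORR | Alpha |
|---|---|---|
| 0 | 10.0% | 1.3% |
| 1.25% | 11.1% | 2.2% |
| 2.5% | 12.25% | 3.3% |
| 5% | 14.5% | 6.7% |
| 10% | 19.0% | 18.2% |

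Alpha reaches 2.5% at p = 0.1149, so f × s = (0.1149 − 0.10)/0.90 = about 1.7%. In an arm of 21 with a true 10% rate, that is 21 × 0.90 × 0.0166 = about 0.3 subjects.

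**5. Where the 21-subject rule applies.** Protocol 3.3 gives 53 Part 2 subjects over six arms. Since 3 × 21 = 63 exceeds 53, at most two arms can reach 21. In other arms that entered Stage 2, the decision rests on whether the lower limit exceeds 10%, where one responder can also matter.

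**The case against.** The strongest reply is that the SAP already excludes these scans. The protocol treats palliative radiation as a form of cancer therapy: the synopsis and Protocol 6.9 list it as an exception to prohibited anti-tumor treatment, not as something else. A programmer could therefore class it as subsequent anticancer therapy. The second exclusion speaks of reduction as well as removal and of unknown pathology, and an irradiated, unresected lesion has no pathology. Appendix D also refers to intervention-therapy and treatment sites, not only to surgery. SAP 6.11 already censors the evaluable lesion sets at non-study anticancer therapy.

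These readings are possible, but none is assured. Protocol 6.9 carves palliative radiation out as permitted treatment, so it need not be coded as a subsequent therapy. The pathology wording follows Appendix D's text on resected lesions. Appendix D's partial-reduction text also says that a lesion still identifiable is measured and response determined; if radiation counts as such an intervention, the shrinkage is counted.

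Parts of the reply stand. A reader might infer that the SAP deliberately keeps post-radiation scans in BOR; it does not say so, it is silent. A reader might also infer that irradiating target lesions is expressly allowed; that rests on the absence of a restriction, and the Protocol 6.9 conditions make it less common. The Appendix D paragraph on earlier local treatment carries no date limit in its own words, so it is not settled that an irradiated target lesion stays in the sum. Nothing in the documents shows that the lesions likely to be irradiated are the injected or target ones.

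**Conclusion.** The point holds as an unclosed gap in the primary endpoint definition. Radiotherapy to a target lesion is not ruled out, no text reliably removes the later scans from BOR and ORR, and so radiation shrinkage can be counted as response to study treatment. The direction is upward. The size is unknown: the alpha figures rest on assumed f and s, and the two-lesion case is constructed. What follows from the documents' own decision rule is that one misattributed responder can separate failure from success (5/21 against 6/21) or stopping from continuing (1/10 against 2/10).

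It would go too far to say that ORR is biased in this trial. The documents do not report how often target lesions were irradiated, and one response separating 5/21 from 6/21 is true of any misclassification.

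The PFS mismatch needs no assumption: Protocol 6.9 counts palliative radiation as clinical progression, and the SAP definition does not include it. SAP Section 10 lists no change from the protocol-specified analyses.

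**What to change.** - **BOR and ORR (SAP Section 5).** State that visit responses other than PD on or after radiotherapy to a target or new measurable lesion are not included, mirroring the rule for resection with tumor present or pathology unknown. New measurable lesions belong in the rule because they are part of the tumor burden.
- **Maximum tumor burden decrease and lesion-level response.** Apply the same cut-off.
- **PFS.** Reconcile the SAP definition with Protocol 6.9, and record any difference in SAP Section 10.
- **Protocol.** Reconcile 6.6 with 6.9 on when palliative radiation is permitted, so that the SAP rule refers to one consistent text.

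**Cost.** A few SAP sentences before the database lock for the primary analysis, with no change in sample size. With post-radiation responses excluded, the design keeps its stated alpha of 1.3% and power of 88.4%. Protocol 6.6 already requires radiotherapy to be entered on the CRF, but the documents do not say that the entry identifies the lesion, so records may have to be mapped to lesions. A few subjects may also lose a response that was truly due to study drug; this makes the rule conservative.
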